COMIRB Protocol

COLORADO MULTIPLE INSTITUTIONAL REVIEW BOARD
[name] [contact] [contact]

Protocol #: 21-3969

Project Title: The Influence of Combined Oral Contraceptives on Weight, Body Composition, Eating Behaviors, and Appetite in Pre-menopausal Women with Overweight or Obesity

Principal Investigator: [name]

Version Date: 5/10/2022

HYPOTHESIS AND SPECIFIC AIMS

The overall objective of this feasibility pilot study is to prospectively evaluate the effects of initiating a combined estrogen and progestin oral contraceptive (**COC**) compared to non-hormonal contraceptives (**NHCs**) on body weight, body composition, eating behaviors, and appetite in pre-menopausal women with overweight or obesity.

Our overall hypothesis is that initiation of COCs in women with overweight or obesity will be associated with greater weight gain and increases in cardiometabolic health risks than use of NHCs over 6 months. We will recruit pre-menopausal women with overweight or obesity who have already elected to initiate COCs through the Comprehensive Women's Health Center (CWHC) as well as a control group comprised of age and BMI matched NHC users. We will evaluate the feasibility of recruiting women initiating a COC and women using NHCs from both the CWHC and the general population into a prospective, observational study as well as the feasibility of evaluating changes in weight, body composition, eating behaviors, and appetite over 6 months from COC initiation. I propose the following specific aims:

Aim 1: Assess the feasibility of recruiting and retaining a racially/ethnically diverse group of pre-menopausal women with overweight or obesity initiating COCs compared to age- and BMI-matched NHC users. We aim to recruit ~10 women per month for 6 months (N=64; n=32 COCs, n=32 NHCs; >20% in each group of African American or Hispanic race/ethnicity) and assess feasibility of completion of outcome measures. We hypothesize that at least 80% of participants will continue their chosen contraceptive method and complete outcome measures within a 2-week window at 6 months.

Exploratory Aim 2: Explore the influence of COC vs. NHC use on body weight, body composition, and cardiometabolic risk factors. We hypothesize that women with overweight or obesity initiating COCs will exhibit greater increases in body weight, fat mass, homeostatic model assessment for insulin resistance (HOMA-IR), triglycerides, and blood pressure compared to age- and BMI-matched NHC users.

Exploratory Aim 3: Explore the influence of COC vs. NHC use on energy intake (EI), eating behaviors, and appetite. We hypothesize that women with overweight or obesity initiating COCs will have greater increases in dietary energy and fat/carbohydrate intake, hunger, disinhibition, reward-based eating, emotional eating, binge eating, and food cravings at 6 months compared to age- and BMI-matched NHC users.

RESEARCH METHODS

A. Outcome Measure(s):

Feasibility Outcomes: *Feasibility of recruitment/enrollment* will be assessed by evaluating the number of patients who express interest, eligibility rate, and enrollment rate. *Retention* will be assessed as number of participants who remain on their contraceptive method and who complete the study divided by number enrolled. *Feasibility of completion of outcome measures* will be assessed as the number of participants completing the study outcome measures at each time point within a 2-week window divided by number of active participants.

Anthropometrics: Anthropometrics will be collected at 0, 3, and 6 months. Gowned body weight will be measured in the morning in a fasted state using a digital scale accurate to ± 0.1 kg. Height will be measured to the nearest 1 mm with a stadiometer at baseline to calculate BMI. Blood pressure will be measured with a manual sphygmomanometer. Fat mass (FM) and lean mass (LM) will be measured with DXA (Hologic Horizon W, version Apex 5.6.04). A review of the electronic medical record (EMR) for clinic weights over the previous 12 months before starting contraception will also be performed.

Outcome Questionnaires: Questionnaires will be administered at 0, 3, and 6 months. Cognitive restraint, unrestrained eating, and emotional eating will be assessed with the Three Factor Eating Questionnaire-Revised 18v^{27,38}. The Reward-Based Eating Drive Scale will be utilized to assess preoccupation with food, loss of control over eating, and lack of satiety³⁹. The Palatable Eating Motives Scale will be administered to measure tendency to use palatable foods to cope with negative feelings⁴⁰. The Trait Food Craving Questionnaire will measure behavioral, cognitive, and physical aspects of craving for different foods⁴¹. The Binge Eating Scale will be used to identify the presence and severity of binge eating behaviors⁴². The Perceived Stress Scale will be used to measure levels of stress on the participant within the past month^{43,44}. The Life Events Questionnaire will be used to assess number of life stressors and the level of effect of these stressors^{45,46}. Interval History questionnaires will be administered at months 3 and 6 to capture any changes in birth control method, medical history, and health and exercise history during the intervention.

Dietary Energy Intake and Macronutrient Intake: Dietary EI and macronutrient intake will be quantified using a written 3-day diet record at baseline and 6 months. Dietary intake data will be collected and analyzed using Nutrition Data System for Research (NDS-R) software (version 2019), developed by the Nutrition Coordinating Center (NCC), University of Minnesota, Minneapolis, MN⁴⁷ to determine kilocalorie and macronutrient content of EI.

Visual Analog Scale: Pre- and post-meal hunger and satiety will be measured using visual analog scales (VAS) before and after each meal for the 3-day time period coinciding with the 3-day diet records⁴⁸⁻⁵¹. Data will be collected using smartphone technology with text messaging reminders (linked to the REDCap study database).

Laboratory Assessments: A 12-hour fasting AM blood sample will be obtained at baseline and 6 months and to assess fasting insulin and glucose (to calculate HOMA-IR) as well as lipids. Baseline samples will also be used to analyze for SNVs in genetic loci of estrogen and progesterone receptor genes.

All measures will be assessed as specified below (Table 1).

Table 1. Outcome Measures by Study Month

	Screening	Baseline	3 month	6 month
Consent	x			
H&P	x			
Screening Questionnaires	x			
Anthropometrics (BMI [kg/m^2], WC [cm]) and Vitals (BP)	x	x	x	x
Body Composition (DXA)		x		x
Lab Collection: Glucose, Insulin, Lipids		x		x
Lab Collection: SNV Analysis		x		
Outcome Questionnaires		x	x	x
3-day Diet Diaries		x		x
Dietary Adherence with VAS		x	x	x

B. Description of Population to be Enrolled:

The study will be performed in a cohort of up to 64 females of reproductive age, age 18-40 years, with overweight or class I and II obesity (BMI 25-39.9 kg/m²) who are seen at the Comprehensive Women's Health Center (CWHC) or a University of Colorado Hospital Anschutz Outpatient Pavilion (UCH AOP) contraception clinic to initiate COCs and women from the CWHC or general population who are using NHCs. Participant inclusion age will be capped at 40 years old to avoid including women in the peri-menopausal phase. Pre-menopausal status will be confirmed by an MD. To be eligible to participate in this observational, feasibility pilot study, volunteers must meet the following inclusion and exclusion criteria:

Inclusion Criteria

- Females
- Age 18-40 years
- Overweight or class I and II obesity (BMI 25-39.9kg/m²)
- Free of major psychiatric illnesses
- Electing to start the Sprintec (norgestimate/ethinyl estradiol 0.25mg/35mcg) COC
- Using non-hormonal forms of contraception: copper intrauterine device (Cu-IUD), male condoms, tubal ligation, partner vasectomy, withdrawal/natural family planning, spermicide, abstinence, or other NHCs as determined by PI

Exclusion Criteria

- Diabetes
- Use of medications thought to affect body weight, energy intake, glycemic parameters, or estrogen (i.e. systemic glucocorticoids, stimulants, weight loss pharmacotherapy, metformin)
- History of weight loss surgery
- History of polycystic ovarian syndrome
- History of congenital adrenal hyperplasia
- Use of a different COC or hormonal contraception method within the past 3 months
- Planning pregnancy
- Planning to stop contraceptive within the next 6 months
- Planning to change diet or join a weight loss program or research study within the next 6 months
- Recent therapeutic abortion or miscarriage in the past 1 month if fetal gestational age <10 weeks, or 3 months if fetal gestational age >10 weeks
- Pregnancy with delivery in the past 6 months
- Currently lactating
- Transmen who were assigned female at birth and either currently using or planning to use gender-affirming hormone therapy in the next 6 months
- Use of other forms of reproductive hormones such as testosterone or dehydroepiandrosterone (DHEA)
- Current tobacco use

C. Study Design and Research Methods

Overview: This study will be performed at the CWHC, the University of Colorado Anschutz Medical Campus (CU-AMC), and the University of Colorado Hospital Anschutz Outpatient Pavilion (UCH AOP). The primary outcome of this pilot and feasibility study is to determine the feasibility of recruiting and retaining a racially/ethnically diverse group of pre-menopausal women with overweight or obesity initiating COCs from the CWHC as well as age- and BMI-match NHC control from the general population. We aim to recruit ~9-10 women per month for 6 months (N=64; evenly distributed as n=32 COCs and n=32 NHCs). We will do a nested subject selection based on race/ethnicity in a 1:1 ratio per group with the goal of including >20% women in each group of African American or Hispanic race/ethnicity. Outcome measures will be performed at the Clinical and Translational Research Center (CTRC) Core Lab and the Colorado Clinical Translation Science Institute (CCTS) Bionutrition Core located at CU-AMC.

Rationale and Justification for Study Design: Contraceptive decision-making is a highly personal process and women often have strong preferences on their contraceptive choice based on contraceptive attributes⁵². It would be unethical to counsel against or withhold contraception from women seeking birth control or deliver a COC placebo. Since NHCs do not contain any synthetic reproductive hormones, NHCs serve as the ideal control for this study. To avoid large drop-out rates in this study, participants in the COC arm will only be enrolled in this study if they elect to initiate COCs (or remain on NHCs) after consultation and thorough contraceptive-counseling with a medical provider at CWHC; they will not be randomized to COC vs. NHCs. We recognize there may be differences in baseline characteristics between women electing to initiate COC versus those who use NHCs. If present, we will adjust for these differences in our analyses.

Study Participants: Participants will be recruited into this *observational* study after they have elected to initiate contraception and selected their contraception method via standard of care. Females of reproductive age (18-40 years old), with overweight or class I and II obesity (BMI 25-39.9 kg/m²) who are using NHCs or who have an established clinical relationship with providers at the CWHC or UCH AOP and have elected to initiate contraception with COCs will be included in the study. [name] (co-mentor) and his research team have extensive experience conducting clinical trials with contraception, including recruiting and enrolling current contraceptive users and new contraceptive users. The CWHC is the primary site for [name] research activities through the NICHD Contraceptive Clinical Trials Network and the recruitment methods described for this study are similar to how this team recruits for novel contraceptive method trials and extension trials of current contraceptive users. As CWHC is a family planning focused clinic, it is an ideal recruitment site for a study of contraceptive method initiators. [name] also has two partners with contraception clinics in the UCH AOP who can offer help recruiting potential participants by distributing fliers with information about the study. Women electing to start Sprintec (norgestimate/ethynodiol 0.25mg/35mcg) will be included in the COC group. Sprintec is the most commonly prescribed monophasic COC at the CWHC and includes a 3rd generation progestin of lower androgenicity⁵³; approximately 80 women are prescribed Sprintec per month. In comparison, women using NHCs (including Cu-IUD, male condoms, tubal ligation, partner vasectomy, withdrawal, and abstinence) will be included in the NHC group. The use of NHCs in the general population of reproductive-aged women who are sexually active is estimated to be 40%⁶.

Recruitment and Screening: Women who are seen for a standard-of-care in-person or telehealth clinical visit for contraception counseling and initiation at the CWHC or UCH AOP who elect to start Sprintec and meet study age and BMI criteria will be asked about interest in participating in this observational study. Women who are seen for routine care in other University of Colorado outpatient clinics and who elect to start Sprintec and who meet age/BMI criteria will be given study fliers and study staff contact information to participate in this observational study. Both potential COC users and NHC users will be recruited from the general population through a combination of e-mail bulletins, printed fliers, and social media. If a woman from the general population meeting age/BMI criteria expresses interest in initiating a COC, she will still be referred to the CWHC or UCH AOP for a standard-of-care in-person or telehealth contraceptive counseling visit and medical examination. After shared-decision making with a provider, if she still elects to start Sprintec, then study staff will reach out to the potential participant for enrollment into this observational study. If women using NHCs meet age and BMI criteria when presenting to CWHC or UCH AOP and elect to remain on NHCs, they will also be asked about interest in participation in this study. Women who are interested in enrolling in this observational study will then undergo an in-person, telephone, or telehealth screen by the study PRA or PI to confirm eligibility and provide an overview of the study. Participants will be asked to sign an eConsent if they agree to participate in the study either in-person on a computer or tablet with a member of the study team present, or on their home device (computer, laptop, tablet, etc.) if study and consent is reviewed via phone or Zoom. If a participant declines eConsent, they will be given the option to sign a paper consent in-person or remotely and email their signed consent to the study team. After providing informed eConsent, participants will be brought to the CTRC for baseline measures and blood draw. A review of the electronic medical record (EMR) for clinic weights

over the previous 12 months before starting contraception will also be performed after consent. Selected contraceptive method will be initiated after baseline measures are collected.

Compensation: Subjects will be compensated for their time and effort in the study. Subjects will receive \$100 for completing all assessment measures at baseline, 3-month, and 6-month follow-up visits.

D. Description, Risks and Justification of Procedures and Data Collection Tools:

Overview of Risks: Risks of study-related complications will be reduced by carefully selecting participants for inclusion in this study. We have clearly defined the contraindications to participation. Every effort will be made to minimize risks including a review of participants' health before study initiation. The study physician will contact the primary care physician of a participant, as needed, to clarify any issues that arise. The risk of finding a previously undiagnosed medical condition will be explained clearly as part of the informed consent, with the possibility that the condition(s) might require follow-up evaluation and treatment. This study will be scheduled to minimize time lost from work or studies, and subjects will receive some compensation for the time involved in completing the outcome measures detailed herein. Members of the research team, including the nursing staff at the CTRC, are trained and experienced in all of the methods and measures that will be performed. These measures will be performed in a controlled clinical environment (the CTRC) with access to a full complement of hospital services. Patients without significant co-morbidities will be recruited for this study to minimize the risks of serious adverse events, as discussed in the *Data and Safety Monitoring Plan*.

Risks of DXA Scan: All participants will undergo two DXA scans to assess body composition. The DXA procedure involves exposure to ionizing radiation. During the DXA, the effective radiation exposure is approximately 0.3 mrems per total body scan. The radiation exposure for the total study will be 0.6 mrems, which is below the annual body radiation exposure of 5,000 mrems permitted for radiation workers by federal regulation. It is possible that the study team will incidentally identify potential bone disorders (i.e., osteoporosis) and follow up testing will be recommended by the study MD.

Minimizing Risks Associated with DXA: To minimize the risk of radiation exposure from the DXA scan trained technicians conduct will conduct all scans, thus, reducing the likelihood of repeat assessments. If non-diagnostic evidence of osteoporosis is identified during the whole-body scan, the study physician will notify the participant and recommend further testing.

Risks of Screening: The primary risk from screening measures is diagnosis of a previously unknown disease. If a previously undiagnosed disease is found during screening or during any of the procedures, the study doctor will discuss the diagnosis with the participant and refer the participant to their primary care provider.

Minimizing Risks Associated with Screening: Every effort will be made to minimize risks including a review of participants' health before the testing. The study physician will contact the family physician, as needed, to clarify any issues that arise. The risk of finding a previously undiagnosed medical condition will be explained clearly as part of the informed consent, with the possibility that the condition(s) might require follow-up evaluation and treatment. This study will be scheduled to minimize time lost from work or studies, and subjects will receive some compensation for the time involved in completing the studies detailed herein.

Risks of Venipuncture: Each time blood is drawn about 1 tablespoon will be removed by putting a needle into the vein. This is the standard medical method used to obtain blood for tests. Subjects will feel pain when the needle goes into the vein but should not feel any after it is in the vein. A bruise may form at the site after the needle is removed. There is also a slight chance you may become light-headed or faint during this procedure.

Minimizing Risks Associated with Venipuncture: To minimize the risks associated with venipuncture, all procedures will be conducted by trained personnel.

Risks of Anthropometric Measures: There are no risks associated with these procedures.

Outcome Questionnaires: Some questionnaires include questions that may make some participants uncomfortable but would not be expected to pose any risk to subjects.

Minimizing Risks Associated with Outcome Questionnaires: Participants will be advised that they do not have to answer any questions that make them uncomfortable.

Risks of Confidentiality and Privacy: The use of questionnaires and collection of personal medical information poses a risk to confidentiality and privacy and may cause embarrassment. However, we foresee no psychological, social, or legal risks beyond those of participating in a health-related research study. There are no alternatives that would permit the acquisition of the information required.

Minimizing Risks Associated with Confidentiality and Privacy: These risks will be minimized by not including personal identifying information on the forms, when possible, and by conducting interviews and collection of personal information in a private setting.

Data Monitoring and Safety Plan: This pilot study aims to evaluate feasibility of recruiting women initiating a COC from the CHWC/UCH AOP or using a NHC into a prospective, observational study as well as the feasibility of evaluating changes in weight, body composition, eating behaviors, and appetite over 6 months from COC initiation (or 6 months of NHC use). The measurement protocols pose minimal risk to patients. Because of this low-risk status, the data safety monitoring plan for this feasibility pilot focuses on close monitoring by the PI (an MD with current board certification in Endocrinology) in conjunction with 3 other MDs who will serve as mentors to the PI and are board certified either in Endocrinology or Obstetrics and Gynecology. All mentors have served as PIs of numerous federally funded projects and are familiar with CU-AMC's safety monitoring protocols.

Measurement and Reporting of Adverse Events: We will collect adverse event data on a case-by-case basis. Adverse events will be reviewed, collated, and evaluated by the PI within 72 hours. All serious adverse events will be evaluated by the PI and mentors within 24 hours. Serious adverse events are defined as: death, life threatening injuries, inpatient hospitalization, persistent or significant disability/incapacity, or congenital anomaly/birth defect. Serious adverse events that are definitely or probably related to the protocol and any unanticipated adverse events that are definitely or probably related to the protocol will be reported to COMIRB and the CTRC within 5 days using the COMIRB Unanticipated Problem Report Form. Any study-related serious adverse events and any deaths (regardless of relatedness) will be reported to COMIRB. All other adverse events will be documented by standard COMIRB procedures.

Monitoring for Out-of-Range Laboratory Values: Laboratory data is collected in this study at two timepoints in this study (baseline and 6-months). Laboratory data (glucose, insulin, and a lipid panel) will be reviewed by the PI and out-of-range values will be reported to the subject. SNV analysis will be run on stored lab samples from baseline blood draws if funding allows. This genetic data will not be reported to the subject and is for hypothesis-generation.

Data and Quality Management: The principal investigator will be responsible for conducting this study, including overseeing participant safety, and complying with all reporting requirements to COMIRB. The investigative team will be trained in accordance with both COMIRB and HIPAA compliance issues and will act to maintain confidentiality and protect health information. Electronic data will be stored on secure servers with a high level of security, controlled access, daily back-up, and long-term retention of back-up files. Clinical data, including adverse events, concomitant medications, comorbidities, laboratory data, and study-specific outcomes will be entered into REDCap. All questionnaires will be collected using REDCap, thus negating the need to enter data from paper questionnaires. REDCap includes password protection and internal quality checks, such as automatic range checks, to identify data that appear inconsistent, incomplete, or inaccurate. Study documents will be retained for a minimum of 7 years as per HIPAA regulations. Any hard copies of study data will be kept in participants' charts in a locked and secured file cabinet in the PI's or Study Coordinator's office. Access to all study data will be restricted to the PI and research personnel. While the study staff and the PI cannot be blinded to participant group assignment and outcome measures,

blinding will occur whenever possible to minimize bias. For example, the CTRC staff collecting labs or performing DXAs will be blinded to participant group assignment. Those scoring questionnaires and the personnel at the CCTSI analyzing diet diaries will also be blinded to group assignment during analysis. Finally, the statistician will be blinded when analyzing outcome measures. Field and range checks will be programmed to minimize data entry errors. Data distribution will be checked periodically, and outliers verified; missing data will be tracked and checked.

Stopping Rules, Withdrawals, and Terminations: In this minimal-risk observational pilot and feasibility study, it is unlikely that excessive adverse events will require stopping the study. However, as outlined above, we will monitor adverse event rates in all participants and alert COMIRB if a larger than reasonably expect adverse event rate should occur. Safety stopping rules will be determined by the PI and her co-mentors and will relate to the risk-to-benefit ratio. All withdrawals and terminations will be reviewed by the PI and research team involved in this study on a case-by-case basis. The data will be evaluated separately to assess for association of contraceptive choice and specific adverse event outcome. An individual subject may be terminated from the study if the volunteer requests to leave the study, evidence of deliberate non-compliance, if the volunteer discontinues or switches their selected contraceptive method or becomes pregnant during the study. Other causes for termination include development of a chronic condition or acute condition likely to impact upon metabolic variables, require medications likely to impact upon metabolic variables, or impair the ability of the subject to participate.

E. Potential Scientific Problems:

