For feasibility *Aim 1*, we hypothesize that at least 80% of participants will continue their chosen contraceptive method and complete outcome measures within a 2-week window at 6 months. Enrollment rate will be calculated as the number of enrolled patients divided by the number of screened and eligible prospects. Retention rates and rates of completing outcome measures at baseline and follow-up visits will be tabulated using the number of enrolled participants as the denominator. A 95% confidence interval (CI) for these rate estimates will be calculated using Copper-Pearson exact method. These analyses will be conducted globally and by study groups.

Precision of Estimates: With a total sample size of 60, 50, and 25, the error margins (i.e. half of the width of a 95% CI for a proportion) will be at most 0.14, 0.15, and 0.2, respectively. These error margins are estimated assuming the observed proportion to be 0.5 (i.e. the most variable case).

For *Aim 2*, we hypothesize that women with overweight or obesity initiating COCs will exhibit greater increases in body weight, fat mass, HOMA-IR, triglycerides, and blood pressure compared to women using NHCs. Each exploratory outcome (body weight, body composition, blood pressure, lipids, and HOMA-IR) will be analyzed using the LMM. The contrast of the change score between baseline and 6 months is of primary interest. For body composition data, the above LMM analysis will be applied after isometric log ratio (iLR) transformation of the outcome (i.e. CoDA analysis). We will also use any weights retrieved from the EMR to assess weight trajectory prior to COC start and compare this to weight gain trajectory after COC initiation or continued NHC use from study start.

Power and Sample Size Calculations: Thirty-two participants in each group will be enrolled at baseline. Accounting for 20% attrition by month 6, a sample size of $n=25$ per group will provide 80% power at 5% significance to detect a between-group difference of 0.81 standard deviation (SD) of the individual change score. In the 2001 Coney et al.⁷ study that followed weight changes with COC use out to 6 months, the SD of weight change at 6 months was 2.6 kg. Assuming a similar SD in our study, we will have sufficient power to detect a 2.4 kg between-group difference in weight change at 6 months, which is of clinical significance.

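### Selecting women on race/ethnicity toward the >20% goal, with no planned figure for the pool they come from, leaves the diversity result and possibly the enrollment rate hard to interpret

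*Combined protocol and SAP*

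**What the plan says.** The Overview in section C defines the primary outcome: "The primary outcome of this pilot and feasibility study is to determine the feasibility of recruiting and retaining a racially/ethnically diverse group". Aim 1 attaches a number to that diversity: "N=64; n=32 COCs, n=32 NHCs; >20% in each group of African American or Hispanic race/ethnicity". The Overview then describes how the sample will be steered toward it: "We will do a nested subject selection based on race/ethnicity in a 1:1 ratio per group with the goal of including >20% women", meaning women from those two populations within each group.

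Section A lists the recruitment measures as "evaluating the number of patients who express interest, eligibility rate, and enrollment rate". The Aim 1 paragraph of section F gives the formula: "Enrollment rate will be calculated as the number of enrolled patients divided by the number of screened and eligible prospects". Rates are to be reported overall and by contraceptive group, with exact 95% confidence intervals. Neither section plans a breakdown by race/ethnicity.

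The only Aim 1 hypothesis with a threshold concerns something else, namely that "at least 80% of participants will continue their chosen contraceptive method and complete outcome measures within a 2-week window at 6 months".

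Recruitment and Screening (section C) goes from interest to eligibility screen, consent and baseline visit. It mentions no race/ethnicity step and does not say when the selection takes place.

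**The concern.** The study selects on the same characteristic that it reports as a feasibility result. If the enrolled groups reach the goal, that could be because the clinics and general-population channels supply enough African American and Hispanic women, or because the team screened until enough were found. The planned tables could not separate the two, and the larger cohort foreseen in section G would need to know which it was.

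The enrollment rate has a related weakness. Its denominator is every screened and eligible woman, with no exception for one whom the study chose not to enroll. If that happens, she is counted like a woman who said no, and the rate mixes willingness to join with the study's own choices. The same applies to an eligible NHC user left out because she does not match on age or BMI.

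The ratio adds to the uncertainty. Equal race/ethnicity strata within a group would give 16 of 32, or 50%, which sits oddly with a goal of more than 20%. If it means matching between groups, the NHC share follows the COC share and is not a separate finding.

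**Working it through.** **Inputs from the documents.** 32 women per group; goal above 20% per group; enrollment rate = enrolled / (screened and eligible). The group size reproduces: 25 evaluable / (1 − 0.20) = 31.25, rounded up to 32.

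**Inputs assumed.** The share p of African American or Hispanic women among eligible women is not given, so a range is used. No selection rule is given either. For illustration, 7 places per group are held for these women, and every eligible woman is willing.

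**Step 1: the goal as a count.** 0.20 × 32 = 6.4. Six women would be 6/32 = 18.8%, seven would be 7/32 = 21.9%. The goal means at least 7 per group.

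**Step 2: chance of reaching the goal with no selection.** For one group this is P(X ≥ 7) with X ~ Binomial(32, p). For both groups, taken as independent, it is the square.

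**Step 3: enrollment rate if 7 places are held.** Let m be the number of African American or Hispanic women among the first 32 eligible. If m is 7 or more, nobody is passed over. If m is below 7, a further (7 − m)/p eligible women are needed on average. So

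E(eligible women seen) = 32 + Σ (m = 0 to 6) P(X = m) × (7 − m)/p,

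and the enrollment rate is about 32 / E. A simulation of the same rule (20,000 runs per value of p) agrees.

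| Assumed share p | Goal met unaided, one group | Both groups | Mean eligible women seen per group | Mean not selected | Enrollment rate |
|---|---|---|---|---|---|
| 10% | 3.6% | 0.1% | 70.1 | 38 | 46% |
| 15% | 19.5% | 3.8% | 47.7 | 16 | 67% |
| 20% | 46.5% | 21.6% | 38.1 | 6 | 84% |
| 25% | 72.2% | 52.1% | 34.1 | 2 | 94% |
| 30% | 88.7% | 78.7% | 32.6 | 0.6 | 98% |
| 40% | 99.1% | 98.2% | 32.0 | about 0 | about 100% |

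For example, at 10% the rate is 32/70.1 = 46%, although no woman has declined.

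**Step 4: how far selection can carry the goal.** If at least 7 are needed from a fixed number of willing eligible women, the chance is P(X ≥ 7) with X ~ Binomial(number willing, p). The numbers of eligible women below are assumptions.

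| Eligible women per group | Consent | Willing | p = 10% | p = 15% |
|---|---|---|---|---|
| 100 | all | 100 | 88% | 99.5% |
| 80 | all | 80 | 70% | 97% |
| 100 | half | 50 | 23% | 64% |
| 80 | half | 40 | 10% | 39% |

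With full consent, selection usually delivers the goal from a pool at half the target share. With half consent it usually does not.

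**The case against.** A reader might infer that selection guarantees the >20% share and that women passed over are recorded as failed enrollments. The documents do not support either statement as fact. They describe no quota, cap, full stratum or eligible woman turned away. Selection by targeted outreach, or before screening, would never enter the enrollment-rate denominator. The share is also not wholly in the team's hands: it depends on consent and on how many eligible women are reached during the planned six months of accrual, and Step 4 shows that the goal can be missed.

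Nor is >20% a success criterion. It is worded as an aim or goal with no decision rule attached. Asking whether a study that recruits deliberately toward a diversity goal can reach it is a legitimate feasibility question, so replacing it with a test of the untargeted pool against 20% would be a matter of preference. The planned counts of interest, eligibility and enrollment also give some view of recruitment effort.

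All of this stands, and it limits the claim. It does not supply what is missing. The planned counts are not split by race/ethnicity, so they cannot show the share in the pool or the effort needed to reach the goal. Because the selection step is undefined, a reader of the results could not tell whether the enrollment rate was affected.

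**Conclusion.** The point holds in a conditional form. As planned, the achieved share cannot show on its own whether the recruitment channels yield a diverse sample, because subjects are selected on race/ethnicity and the composition of the interested and eligible women is not reported. This part follows from the text alone.

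The effect on the enrollment rate holds only if selection or matching takes place at or after the eligibility screen. Its size rests on the assumed pool share, on 7 of 32 places being held, and on full willingness: about 46%, 67% and 84% at shares of 10%, 15% and 20%, and 94% or higher from a share of 25%. If the pool is that diverse, the enrollment rate is little distorted, but no planned figure would show that this was so. The change is worth making, since it is cheap and the information may not be recoverable once screening has ended.

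**What to change.** 1. In Aim 1 and its paragraph in section F, keep the >20% goal for the enrolled sample. Add the African American/Hispanic proportion, with exact 95% confidence interval, among interested and among eligible women, by contraceptive group, and the number screened to reach the goal.
2. In section F, define the enrollment rate as enrolled divided by eligible women offered enrollment. Report eligible women not offered a place because of race/ethnicity selection or matching as a separate count, apart from those who declined.
3. In the Overview of section C, replace the 1:1 wording with the rule intended, for example a minimum of 7 of 32 per group or race/ethnicity matching between groups, so that it agrees with >20%, and say at what stage it is applied.

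The cost is protocol wording, one screening-log field (race/ethnicity and reason not enrolled) and one extra table, with no added participants or procedures. The drawbacks are reliance on self-reported race/ethnicity at screening and a diversity figure that may look less favourable than the enrolled share.
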